### 3. Generalizability

This study is drawn from a database of privately and publically insured populations. As such, it may not be generalizable to other populations. Similarly, dialysis patients were not included,

---

due to different prescribing patterns among dialysis and potentially different clinical symptoms. Thus, the results of this study may not be generalizable to patients on dialysis.

#### IV. APPENDICES

##### A. APPENDIX 1: DIAGNOSTIC AND PROCEDURE CODES FOR DIALYSIS

ICD-9-CM Diagnosis Codes									
458.21	996.56	996.68	996.73	V45.1	V56				
ICD-9-CM Procedure Codes									
39.95	54.98								
CPT-4 Procedure Codes									
36145	36800	36825	36832	90935	90945	90964	90967	90970	90999
36147	36810	36830	36833	90937	90947	90965	90968	90989	93990
36148	36815	36831	49421	90940	90963	90966	90969	90993	99512
HCPCS Procedures									
A4653	A4709	A4728	A4770	A4911	E1520	E1592	E1635	G0323	G8076
A4671	A4714	A4730	A4771	A4913	E1530	E1594	E1636	G0324	G8081
A4672	A4719	A4736	A4772	A4918	E1540	E1600	E1637	G0325	G8082
A4673	A4720	A4737	A4773	A4929	E1550	E1610	E1639	G0326	G8085
A4674	A4721	A4740	A4774	C1750	E1560	E1615	E1699	G0327	G8714
A4680	A4722	A4750	A4802	C1752	E1570	E1620	G0257	G0365	G8715
A4690	A4723	A4755	A4860	C1881	E1575	E1625	G0320	G0392	G8956
A4706	A4724	A4760	A4870	E1500	E1580	E1630	G0321	G0393	S9335
A4707	A4725	A4765	A4890	E1510	E1590	E1634	G0322	G8075	S9339
A4708	A4726	A4766							

**B. APPENDIX 2: HEALTH PLAN ADMINISTRATIVE AND CLAIMS CODES USED FOR ANAPHYLACTOID REACTIONS**

**ICD-9-CMa diagnosis codes:**

995.0 = Other anaphylactic shock  
995.2 = Other and unspecified adverse effect of drug, medicinal and biological substance (due) to correct medicinal substance properly administered;  
995.3 = Allergy unspecified  
999.4 = Anaphylactic shock due to serum  
E930-E949 = Drugs, medicinal and biological substances causing adverse effects in therapeutic use  
519.11 = Acute bronchospasm  
786.1 = Stridor  
458.9 = Hypotension unspecified

**2009 HCPCSb codes:**

J0170 = Injection, adrenalin, epinephrine, up to 1 ml ampule  
J0171 = Injection, adrenalin, epinephrine, 0.1 mg  
J1200 = Injection, diphenhydramine hcl, up to 50 mg

**CPTc code:**

92950 = CPR

**ICD-9-CM procedure code:**

99.60 = CPR

a International Classification of Diseases, Ninth Revision, Clinical Modification

b Healthcare Common Procedure Coding System

c Current Procedural Terminology

**C. APPENDIX 3. FINAL ALGORITHM FROM THE MINI-SENTINEL ANAPHYLAXIS VALIDATION WORKGROUP TO IDENTIFY POTENTIAL CASES OF ANAPHYLAXIS USING ICD-9-CM DATA.**

**Criterion A:** (995.0 [other anaphylactic shock] or 999.4 [anaphylactic shock due to serum]) inpatient or emergency department encounter

**OR**

**Criterion B:** (995.0 [other anaphylactic shock] or 999.4 [anaphylactic shock due to serum]) outpatient encounter **PLUS** a code for one of the following symptoms/procedures/treatments:

- i. bronchospasm (519.11) or
- ii. stridor (786.1) or
- iii. hypotension (458.9) or
- iv. epinephrine (J0170 or J0171) OR
- v. injection of diphenhydramine (J1200) or
- vi. CPR (92950 or 99.60)

**OR**

**Criterion C:** (995.3 [allergy unspecified] or 995.2 [other unspecified adverse effect of drug] or E930-E949 [drugs, medicinal and biological substances causing adverse effects in therapeutic use]) inpatient or emergency department encounter

- i. **PLUS** a code for one of the following symptoms/procedures/treatments:
  1. bronchospasm (519.11) or
  2. stridor (786.1) or
  3. injection of diphenhydramine (J1200)
- ii. **and ALSO** a code for one of the following symptoms/procedures/treatments:
  1. hypotension (458.9) or
  2. epinephrine (J0170 or J0171) or
  3. CPR (92950 or 99.60)

For inpatient and ED codes: All patients who met inclusion criteria were sampled.

For outpatient encounters: All patients who met inclusion criteria, excluding patients with an encounter in the prior 30 days that documented an anaphylaxis code (995.0 or 999.4) were sampled.

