### B. EPIDEMIOLOGY OF IRON-INDUCED ANAPHYLAXIS/ANAPHYLACTOID REACTIONS

Parenteral iron is available as iron dextran, sodium ferric gluconate, iron sucrose, and ferumoxytol (Table 1). It is commonly used for the treatment of anemia in dialysis, malignancy, inflammatory bowel disease, and anemia due to ongoing blood losses (e.g., gastrointestinal bleeding, menorrhagia, postpartum bleeding). Few published studies have evaluated the risk of anaphylaxis associated with specific preparations of parenteral iron exposure. Only the iron dextran products have a black box warning regarding risk of anaphylactoid/anaphylaxis reactions and a test dose is recommended prior to parenteral administration of iron dextran.

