Barton *et al.* in 2000 performed a study of 135 iron-deficient patients with normal renal function who failed oral iron therapy and were treated with iron dextran; the patients were premedicated with cimetidine, diphenhydramine, and dexamethasone. No patients had anaphylaxis; 13% had mild reactions, including arthralgias and myalgias. Fishbane *et al.* in 1996 performed a study of 573 patients treated with iron dextran (INFeD) at four hemodialysis settings from 1993-1995; ten (1.7%) had anaphylactoid-type reactions.

Auerbach *et al.* in 2004 described an open-label, multicenter prospective randomized trial in 157 anemic patients receiving chemotherapy, comparing subcutaneous erythropoietin to (1) no iron; (2) oral iron; (3) iron dextran repeated bolus; (4) iron dextran infusion. There were 3 patients in the infusion group with adverse events – two delayed myalgia/arthralgia, and one acute hypersensitivity (the hypersensitivity reaction was in a patient receiving a test dose of Dexferrum). Of the bolus patients, one experienced delayed myalgia/arthralgia, one experienced fatigue, and one reported shortness of breath. In the oral iron group, one patient experienced nausea. Auerbach also describes the use of rapidly administered (1 hour) 1 gram low molecular weight iron dextran in 396 iron deficient patients, in which there were no anaphylactoid reactions and no serious adverse events.

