### **B. IDENTIFICATION OF NEW-USERS OF DRUGS OF INTEREST**

We propose to use a “new-user” cohort design. We will identify health plan members with a first administration of a parenteral iron preparation during the period January 1, 2000 to June 30, 2013. We note that not all Data Partners will have data for the entire study period. Use of parenteral iron preparations will be identified using the procedure codes shown in Table 1. We will not identify parenteral iron administration using the National Drug Codes (NDCs), because in a summary table analysis we found the use of IV iron products identified as by NDCs in the Mini-Sentinel Distributed Database to be quite low (~3,000 vs. ~200,000 identified by procedure codes, see Section H). Given that anaphylaxis is a rare event, we decided that this number is too low to identify an adequate number of events among users.

We refer to the procedure date of the first administration of the iron preparation as the *index date*. We will require eligible individuals to meet all of the following criteria during the 183-day period prior to the index date: 1) continuous health plan enrollment with pharmacy and medical benefits; and 2) no administration of any of the parenteral iron products of interest in the emergency department, outpatient (ambulatory) visits, or inpatient visits; and (3) no procedure codes for dialysis (Appendix 1). Dialysis patients were excluded from analysis because they represent less than half of the population receiving parenteral iron in the MSDD, their prescribing patterns appear different from other parenteral iron users, and because dialysis patients may be clinically distinct from other parenteral iron users. Gaps of 45 days or less in enrollment will be ignored because they usually represent administrative gaps rather than actual disenrollment.

The exposure group will be new users of iron dextran. The comparison group will be new users of other parenteral iron products. We will identify use of iron preparations in the inpatient, emergency department, and outpatient settings, although we expect the majority of parenteral iron use to be in the outpatient setting. For patients who may be eligible for more than one new use episode during the study period, only their first eligible episode will be included in the analysis.

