## H. POTENTIAL LIMITATIONS AND ATTEMPTS TO MINIMIZE THEM

### 1. Misclassification bias

Bias could be introduced by the misclassification of the exposure, parenteral iron, or the outcome, anaphylaxis. We will review all cases meeting criteria for anaphylaxis or identified with an administration of epinephrine to minimize misclassification while at the same time using a sensitive measure for more complete capture of cases. We will have two adjudicators independently review all potential cases of anaphylaxis to reduce misclassification of the outcome. This will reduce potential false positives but will not address false negatives. Adjudicators will be blinded to the specific parenteral iron product used. For the exposure of interest, iron dextran, we expect there will be some unavoidable grouping of high molecular weight and low molecular weight forms. However, since the literature indicates that these forms are often confused and substituted in clinical practice, it seems necessary to combine them in our study. As a result, we will not be able to estimate the risk of anaphylaxis separately for high and low molecular weight iron dextran. We will review each chart where the patient developed anaphylaxis in an attempt to ascertain whether the iron dextran agent involved was INFeD or Dexferrum. In addition, for all cases of anaphylaxis we will collect information about whether the patient received premedication (e.g., diphenhydramine, IV fluids, or corticosteroids) and, if so, which medications were used.

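### An outpatient anaphylaxis code reaches chart review only with a second code, and injected diphenhydramine given as premedication can supply it, so case capture may differ between iron dextran and comparators by an unknown amount

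*Protocol*

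**What the plan says.** Section II.C adopts the validation workgroup's algorithm in Appendices 2 and 3 to find potential cases on the day of iron administration or the day after. The algorithm treats care settings differently:

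- Criterion A accepts "995.0 [other anaphylactic shock] or 999.4 [anaphylactic shock due to serum]) inpatient or emergency department encounter" with nothing further.
- Criterion B accepts "995.0 [other anaphylactic shock] or 999.4 [anaphylactic shock due to serum]) outpatient encounter" only with one of six further codes: bronchospasm, stridor, hypotension, epinephrine, "injection of diphenhydramine (J1200"), or CPR. It sets no rule on when or why the diphenhydramine was given.
- Criterion C concerns less specific codes in inpatient or emergency department encounters. J1200 counts there too, but a hypotension, epinephrine or CPR code is also needed.

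On setting, Section II.B says "we expect the majority of parenteral iron use to be in the outpatient setting". Section II.H.1 will record, for anaphylaxis cases, "whether the patient received premedication (e.g., diphenhydramine, IV fluids, or corticosteroids"). Section I.B describes an iron dextran study in which "the patients were premedicated with cimetidine, diphenhydramine, and dexamethasone", and it also says "Only the iron dextran products have a black box warning regarding risk of anaphylactoid/anaphylaxis reactions". Section II.C adds a search for epinephrine on the same or next day. Section II.D aims to validate all potential cases, and Section II.H.1 concedes that chart review does not deal with false negatives.

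**The concern.** Take two outpatients with the same reaction, the same 995.0 code and no qualifying code arising from the reaction. One was premedicated with billed injected diphenhydramine, so the chart is pulled and the case can be confirmed. The other was not, so the chart is never pulled and the patient counts as event-free. What separates them is what was done before the reaction, not the reaction itself.

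If premedication practice differs by product, the sensitivity of case finding differs by exposure group. Adjudication removes false positives, so the ratio of the two sensitivities multiplies the relative risk directly. Propensity scores do not correct this: it is an outcome-detection error, and premedication is not in Tables 4 or 5. Collecting premedication only for anaphylaxis cases would not show afterwards whether capture had differed. Whatever the pattern by product, missed cases also lower the incidence estimates of Section II.G.3.

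**Working it through.** **Can another planned step recover the missed case?**

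1. Chart review is limited to flagged patients, so an unflagged patient is not seen.
2. Epinephrine is already one of the six Criterion B codes. An outpatient with 995.0 or 999.4 who lacks all six has no such epinephrine code for the extra screen to find.
3. Criterion A recovers the patient only if an anaphylaxis code is also recorded in the emergency department or as an inpatient.

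The gap is therefore the outpatient-only case with the anaphylaxis code and none of the six others.

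**How large could the effect be?** The protocol states no figure for this, so all inputs are assumptions:

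- *u*: share of outpatient-coded true cases with no qualifying code apart from premedication J1200; 0.10 to 0.30, the same in both groups.
- *p*: share of users premedicated with billed J1200; 0.50 for dextran and 0.10 for comparators.
- *f*: share of true cases that can be found only through the outpatient route; 1 or 0.5, the same in both groups.

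Capture within the outpatient-coded subset = (1 − u) + u × p.

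Overall sensitivity = (1 − f) + f × [(1 − u) + u × p].

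Observed RR = true RR × (dextran sensitivity ÷ comparator sensitivity).

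| f | u | Dextran | Comparators | Factor on RR | Factor if premedication is reversed |
|---|---|---|---|---|---|
| 1 | 0.10 | 0.90 + 0.10 × 0.50 = 0.95 | 0.90 + 0.10 × 0.10 = 0.91 | 1.04 | 0.96 |
| 1 | 0.20 | 0.80 + 0.20 × 0.50 = 0.90 | 0.80 + 0.20 × 0.10 = 0.82 | 1.10 | 0.91 |
| 1 | 0.30 | 0.70 + 0.30 × 0.50 = 0.85 | 0.70 + 0.30 × 0.10 = 0.73 | 1.16 | 0.86 |
| 0.5 | 0.10 | 0.50 + 0.50 × 0.95 = 0.975 | 0.50 + 0.50 × 0.91 = 0.955 | 1.02 | 0.98 |
| 0.5 | 0.30 | 0.50 + 0.50 × 0.85 = 0.925 | 0.50 + 0.50 × 0.73 = 0.865 | 1.07 | 0.94 |

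With equal premedication in the two groups the factor is 1.00. With f = 1, the cases lost are 5% (dextran) and 9% (comparators) at u = 0.10, and 15% and 27% at u = 0.30.

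**Scale against the plan.** Table 7 is not in dispute. Its first row (baseline risk 2.05 per 10,000, RR 2.80) states 81.3% power; an exact Fisher calculation with the doubled one-sided p-value, using 40,015 and 60,714 users, gives 80.7%. The table's lower baseline risks, 2.05 to 2.65 per 10,000, imply 60,714 × 0.000205 = 12.4 to 60,714 × 0.000265 = 16.1 comparator events. A few missed cases would thus be a visible share of the total. A factor of 1.04 to 1.16 is nevertheless small beside the relative risk of four that Section II.G.7 set as the target, and beside the detectable relative risks of 1.70 to 2.80.

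**The case against.** The link to exposure is thinly documented. The premedication evidence is one iron dextran study, and Section II.H.1 mentions diphenhydramine for anaphylaxis cases in general. Neither place says it was injected, which is what J1200 requires. The boxed warning comes with a recommended test dose, not with premedication. Section II.H.2 says providers may avoid dextran in patients they think are at high risk, which could mean more premedication among comparators. All of this stands: neither direction nor size is established.

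A reader might infer that an unpremedicated outpatient with no epinephrine or diphenhydramine code is never reviewed. The protocol does not support that. Bronchospasm, stridor, hypotension and CPR codes also qualify, and respiratory compromise and reduced blood pressure are central to the clinical criteria in Table 2. Many true cases may therefore carry one of these codes. Cases coded in the emergency department or as inpatients enter by Criterion A.

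A reader might also take the 30-day rule in Appendix 3 ("excluding patients with an encounter in the prior 30 days that documented an anaphylaxis code (995.0 or 999.4) were sampled") as a second loss of cases in this study. Its past tense, under a heading naming the validation workgroup's algorithm, most likely describes how that workgroup drew its charts. Because Section II.C adopts the appendix without qualification, a clarifying sentence is worthwhile, but this is not a demonstrated error.

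Finally, a validated algorithm with a known positive predictive value is a defensible choice, and the protocol openly says that false negatives remain. That disclosure is general, however, and does not identify a source that may be tied to exposure. A second-code filter mainly protects predictive value, which matters less when every flagged chart is to be adjudicated.

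**Conclusion.** The point holds as a gap in outpatient case finding that may be differential. Outpatient-only cases with 995.0 or 999.4 and none of the six further codes are counted as non-cases. Because premedication J1200 can open the route to review, capture can depend on premedication practice.

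The tempting conclusion that the relative risk for dextran will be inflated is not supported: the protocol gives no premedication rates by product. The factor of about 1.04 to 1.16 rests wholly on the assumed inputs and applies within the outpatient-coded subset. It falls to about 1.02 to 1.07 if half of all cases enter by other routes, and goes below 1 if comparators are premedicated more. This is an inexpensive improvement to the plan and does not by itself undermine the primary comparison.

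**What to change.** For this study, amend Section II.C or Appendix 3 so that every outpatient encounter with 995.0 or 999.4 on the day of iron or the day after goes to chart review without a second code. The adjudicators, blinded to product and to how the case was identified, then decide. This removes Criterion B's dependence on premedication, whichever way it runs, and serves the protocol's own aims of greater sensitivity and of validating all potential cases.

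Add a sentence saying that the 30-day prior-code exclusion describes the validation study's sampling and is not applied here. Acknowledge in Section II.H.1 that Criterion C also counts J1200, so a smaller dependence remains in the inpatient and emergency department route.

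The cost is protocol wording, some additional charts and a lower positive predictive value among the outpatient charts reviewed. The extra charts are probably few, because the code must fall within two days of iron, but the protocol gives no count to confirm that.
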